4.3 Follow-up Visits

Participants will be required to return to the study site at Weeks 6 and 12. Each study visit will have a visit window of ±5 days, although the ideal visit date will fall on the exact anniversary date from randomization. Procedures to be performed at these visits can be seen in Attachment 1 (Schedule of Events).

The study assessments to be completed at each visit are outlined below:

Week 6 visit:

- Collection of vitals (including blood pressure, respiratory rate, heart rate, and body temperature)
- Anthropometric assessments (including height, weight, waist and hip circumference)
- Review of concomitant medications and adverse events
- Drug accountability assessment
- Drug dispense from research pharmacy
- laboratory assessments (see Blood Collection Schedule- Attachment 2 for more detail)
- Stool sample collection
- Blood spot collection

Week 12 visit:

- Administration of 3, 24-hour recalls (NDS-R) prior to visit
- PROMIS Questionnaires
- Physical Examination
- Collection of vitals (including blood pressure, respiratory rate, heart rate, and body temperature)
- Anthropometric assessments (including height, weight, waist and hip circumference)
- Review of concomitant medications and adverse events
- Drug accountability assessment
- 2-hour oral glucose tolerance test
- Participant counseling regarding follow-up care
- Fasting laboratory assessments (see Blood Collection Schedule- Attachment 2 for more detail)
- Stool sample collection
- Blood spot collection
- MRI
- Optional Sub-study: Accelerometer data collection for 1 week (prior to Week 12 visit)

Optional Sub-study: Accelerometers

An optional sub-study will be presented to subjects at the time of consent. Participation in this sub-study will be optional and will not be required if subjects are participating in the main study. Actigraph GT3X accelerometers will be given to subjects at the Baseline visit and prior to the Week 12 visit. Study staff will place the accelerometer around the subject's waist over the right hip and instruct them on how to properly replace the equipment after showering. Phone calls will be made to remind the subjects as needed. Subjects will collect 7 consecutive days of data and will bring the device back with them to their next appointment or mail the equipment back in prepaid mailers. A phone interview will be performed at the end of each monitoring period to record any unusual activity or episodes of removal.

4.4 Standardized Questionnaires

A number of standardized questionnaires will be administered at screening and throughout the duration of the study.

Alcohol Use Disorders Identification Test (AUDIT): This 10-item self-report questionnaire will be used at screening in order to determine that no significant alcohol consumption is present among participants.

24 hour food recall (NDSR 2016) - A triple pass, evaluation of current diet. The NDSR will be collected from all participants at the visits indicated in the Schedule of Events (Attachment 1).

Patient Reported Outcomes Measurement Information System (PROMIS) – A highly reliable tool for measuring patient-reported health statues for physical, mental, and social well-being. Selected questionnaires include: pediatric fatigue, depression, and anxiety.

Block Physical Activity Survey (NutritionQuest) – A 9 item screening tool that asks about frequency and duration of activities in the past 7 days.

4.5 Specimens

Plasma samples are all collected in EDTA tubes and plasma is separated within two hours of the blood draw. The samples are aliquoted into tubes and immediately frozen and stored at -80 C. Stool will be stored at -80 C. We will use the Nautilus software, by Thermo Scientific, which is a central laboratory information management system (LIMS) service provided by the ACTSI and Emory research laboratories. The systems facilities the tracking and management of specimens, laboratory inventories, and reagent ordering; the management of lab and QC data; the acquisition of data directly from instruments; and the exchange of laboratory results data. This will allow us to easily store and retrieve samples for future analyses.

4.6 Drug Accountability

In compliance with local regulatory requirements the Investigator or designated staff will document the amount of study drug administered to study participants as well as the amount returned by study participants. The study coordinator and research pharmacist will count all tablets returned by the participants at the visits indicated in the Schedule of Events (Attachment 1). Study drug accountability

logs will be maintained throughout the course of the study. In addition, the study coordinator will call participants in between visits to assess compliance. If study product compliance becomes an issue the study coordinator will discuss the importance of maintaining a proper dosing schedule and will try to identify any problems or barriers that exist in taking the study product. If doses are missed repeatedly, the Investigator will use her clinical judgment to determine the participant's ability to comply with the protocol and whether the participant should continue in the study.

4.7 Participant Retention:

Resources will be utilized to remove barriers to participation such as child or elder care, transportation and parking expenses. These resources may be provided as cash, transportation cost coverage and/or parking passes. An honorarium will be paid to participants in recognition of their time and effort when scheduled visits are completed successfully.

4.8 Management of Concurrent Conditions

During the screening period the PI will review concomitant medications on a case by case basis to determine if there are any potential drug interactions. If there is a potential drug interaction, the participant will not be randomized. Of note, there are no known product/drug interactions for IMM-124E.

4.9 Definitions:

Adverse event is any untoward medical occurrence in a participant participating in a clinical study that does not necessarily have a causal relationship with the study drug. It can also mean any unfavorable and unintended sign (including laboratory findings, symptom, or disease) temporarily associated with the use of IMM-124E or placebo, whether or not directly related to IMME-124E.

Suspected Adverse Reaction: any adverse event for which there is a reasonable possibility that the drug caused the adverse event. All gastrointestinal adverse events that begin within a pre-defined period of administration of the product will be presumptively considered possibly related to the investigational product per FDA recommendation.

Serious adverse event or serious suspected adverse reaction

Any adverse event that:

- Results in death
- Is life-threatening
- Results in persistent or significant disability/incapacity (i.e. a substantial disruption in a participant's ability to conduct normal activities of daily living)
- Is a congenital anomaly/birth defect
- Requires inpatient hospitalization or prolongation of existing hospitalization
- Is an important medical event that, while it may not result in death or be immediately leftthreatening or require/prolong hospitalization, may jeopardize the participant and/or may require medical or surgical intervention to prevent one of the outcomes listed above

Note that hospitalization due to disease progression is considered an SAE. Hospitalization for an elective or planned procedure to treat a pre-existing condition is not considered an SAE unless it results in one of the other outcomes listed above.

4.10 Safety Monitoring and Reporting

The investigators and site staff for this study will monitor and report adverse events to ensure patient safety. All untoward events occurring between the time of obtaining informed consent and following the last visit must be documented, regardless of whether they are considered study-related. The only exception is for participants who have withdrawn informed consent. Any AE that worsens in intensity, or becomes serious, should be recorded as a new event.

The DSMB will have semi-annual meetings where summary data on adverse events will be analyzed. Using Version 3.0 of the National Cancer Institute's Common Terminology Criteria for Adverse Events (CTCAE).81 signs and symptoms associated with adverse events will undergo assessment of intensity and will be graded by the clinical site staff as:

- Mild: Awareness of symptoms that are easily tolerated causing minimal discomfort and not interfering with everyday activities
- Moderate: Sufficient discomfort is present to cause interference with normal activity
- Severe: Extreme distress causing significant impairment of functioning or incapacitation. Prevents normal everyday activities.

The PI will submit a summary of study data findings to the IRB at the time of continuing review. Adverse event aggregate reports will not be submitted to the IRB, except those that involve unanticipated problems that might put participants at risk or protocol deviations.

The Investigator will coordinate with Emory Research Compliance office for the reporting of any and all IND safety reports to the FDA as *per* the requirements outlined in 21 CFR 312.32. A summary of all non-expedited safety reports will be submitted in the annual report.

Adverse events must be reported to the Emory University IRB according to IRB policy. SAEs will also be reported to the DSMB within 2 days or the event of notification of the event.

Protocol Deviations:

The PI and research team intend to not deviate from the protocol except in the case of a medical emergency. However, humans are by nature not perfect and sometimes protocol deviations occur. The [name] research team has instituted internal procedures to minimize protocol deviations. Emory University's IRB will be informed of any protocol deviations that occur according to applicable regulations and the IRB's established procedures.

A summary of adverse events will be reported to the FDA as part of the IND annual report.

Monitoring:

The research team will comply with their Monitoring Plan. This will involve monitoring by a compliance coordinator for the Center for Clinical and Translation Research at Emory University. Informed consents, protocol versions, source documents, CRFs, and AE reporting will be monitored. This will occur after the first two subjects have been enrolled and then will continue minimally once a year, if not more. A minimum of 10% of the subjects will be reviewed at each of the monitoring visits and a report will be provided to the Investigator at the conclusion of each monitoring visit.

4.11 Unblinding Procedures

Under normal circumstances, so as to not compromise the integrity of the study, the blind should not be broken until all participants have completed the study and the database in finalized. Otherwise, the blind should be broken only if specific emergency treatment would be dictated by knowing the treatment status of the participant.

Unblinding and disclosure to the participant, PI, and PCP may occur if any of the following conditions occur:

- Pregnancy (study product discontinued)
- Development of hepatotoxicity (study drug discontinued, unblinding may occur at the conclusion of the study)

If the treatment is unblinded for any participant, the participant will not be withdrawn from the study. The DSMB will review all instances of unblinding. Unblinded subjects will continue to be followed in the trial to allow for an intent-to-treat analysis.

5. Statistical Design and Analysis:

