	improvement in TG/HDL ratio, improvement in insulin resistance, and >10%		
	improvement in ALT		
Study Duration (per	Up to 19 weeks total		
participant):	• Up to 6 weeks screening		
	12 week treatment		
Study Duration (calendar	• Study start-up: 0 – 4 months		
time):	Recruitment phase: 5 -14 months		
	Follow-up phase: 15 - 18 months		
Math Cale a duile :	Analysis and reporting: 18 - 24 months		
Visit Schedule:	Screening Visit		
	Baseline visit		
	Follow up visits		
Ctatistical Analysis	• Week 6 and Week 12 visits		
Statistical Analysis:	Descriptive variables of the cohort and subgroups will be analyzed using means and standard deviations or medians and ranges, as appropriate. Percent change in		
	primary and secondary outcomes will be compared using two sample t-test or		
	Mann-Whitney test. Absolute change over time will be compared using mixed		
	model or analysis of covariance.		
Sample Size:	A sample size of 11 participant per group is required to achieve a least 90% power		
Sample Size.	to detect a 15% point difference in the average % change in ALT from baseline to		
	week 12 between the two groups. Sample size was calculated assuming common		
	standard deviation of 10% using a two-sided Mann-Whitney tests with a 0.05		
	significance level. We will include 20 participants per group to allow for drop out,		
	intra-individual variability and multiple hypothesis testing.		
Safety Monitoring:	A DSMB will monitor the data for safety and efficacy for outcomes such as nausea,		
earcey monitoring.	abdominal pain, flatus, diarrhea, pregnancy, hepatotoxicity and any other outcomes		
	or events identified as safety related.		

Table of Contents

1.1 Primary Objectives71.2 Secondary Objectives72. Background & Significance73. Study Design113.1 Design Overview113.2 Inclusion Criteria113.3 Exclusion Criteria113.4 Rescreening123.5 Treatment Groups123.6 IMM-124E Administration123.7 Recruitment and Retention133.8 Sources and Materials133.9 Potential Risks133.10 Protection Against Risks143.11 Potential Benefits153.12 Data and Safety Monitoring164. Study Plan16
2. Background & Significance.73. Study Design.113.1 Design Overview.113.2 Inclusion Criteria.113.3 Exclusion Criteria.113.4 Rescreening.123.5 Treatment Groups.123.6 IMM-124E Administration.123.7 Recruitment and Retention.133.8 Sources and Materials.133.9 Potential Risks.133.10 Protection Against Risks.143.11 Potential Benefits.153.12 Data and Safety Monitoring.16

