This is a 12 week randomized, double-blind, placebo-controlled "proof of concept" trial (RCT) testing the effect of IMM-124E on change in ALT in children with NAFLD. A placebo-controlled trial was selected because this is the highest quality method and pediatric NAFLD has a substantial placebo response rate (typically ranges from no change to a 30 U/L improvement in ALT at 12 weeks after the initial diagnosis by liver biopsy). Further, a parallel arm trial is necessary because the sustainability of IMM-124E influence is not known and thus the appropriate length of a wash-out period was unclear. ALT is an accepted surrogate marker of hepatic inflammation in children and improvements can be seen within several weeks in pediatric NAFLD⁶.

3.2 Inclusion criteria:

- Age 6 19 years at time of initial screening
- NAFLD diagnosis (confirmed by liver biopsy, MRI, or Ultrasound)
- ALT $\ge 2 \times ULN$ at screening (girls ≥ 46 , boys ≥ 54)
- Written informed parent consent and child assent
- Willingness to consume the investigational product 3 x daily for 12 weeks
- At least 2 months of attempted lifestyle changes after diagnosis

3.3 Exclusion criteria:

- Disease or condition deemed by physician to interfere with absorption, digestion, or mechanism of intervention of drug
- Diagnosis of diabetes and an HbA1c of > 9%
- Change in supplement or anti-oxidant therapy within past 90 days (must be on a stable dose and willing to continue it throughout the trial or not on any vitamin or supplement, includes SAMe, vitamin E, betaine, Milk thistle etc)
- Use of probiotics or antibiotics in the past 30 days
- Use of anti-NAFLD medications (metformin, thiazolidinediones, UDCA) in the 30 days prior to randomization
- Acute illness within past 2 weeks prior to enrollment (defined as fever > 100.4ºF)
- Planned pregnancy, nursing an infant, confirmed or suspected to be pregnant between screening and time of study enrollment
- Evidence of other chronic liver disease other than NAFLD (Hepatitis B and C, Alpha-1 antitrypsin, Wilson's disease)
- Intolerance to lactose or dairy-based products
- Unable to have blood drawn at study visits
- Unwillingness to provide and/or collect stool samples
- Current GI bleeding or inflammatory bowel disease (IBD, colitis)
- Current enrollment in another therapeutic clinical trial or receipt of an investigational study drug within 6 months prior to study enrollment

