- Urine pregnancy test for females of childbearing potential
- Blood spot collection
- MRI (Brief scan for full body and liver fat assessment)

• Optional Sub-study: Accelerometer data collection for 1 week

4.2 Randomization Procedures:

After consent and eligibility for the trial is confirmed, participants will be randomly assigned to either IMM-124E or placebo. The randomization will be assigned by the research pharmacist and will be blocked by age group (6-12 years versus 13-19 years) to ensure balanced groups. The investigators, lab personnel, research coordinators and participants will be blinded to the assignment. The research pharmacy will dispense the similarly appearing IMM-124E and placebo at baseline and again at Week 6.

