7.1 Attachment 1: Study Schedule of Events

	Screening (-6 weeks)	Baseline (Week 0)	Week 6	Week 12
Informed Consent and HIPAA Authorization	X			
Review Inclusion/Exclusion Criteria	X	Х		
Randomization		Х		
Demographics & Medical History	X			
Physical Exam		Х		Х
Vital Signs	X	Х	Х	Х
Standardized lifestyle counseling		Х		
Height	X	Х	X	X
Weight	X	Х	X	X
Waist and hip measurements	X	Х	X	X
Alcohol Use Disorders Identification Test (AUDIT)	X			
24-hour food recalls (NDS-R) x 3	X			Х
MRI	(X ¹)	Х		Х
PROMIS Questionnaires (fatigue, depression, anxiety)		Х		X
Physical Activity Assessment		Х		X
Urine Pregnancy Test		Х		
Oral Glucose Tolerance Test (2-hr)		Х		X
Blood Draw (see Attachment 2)	X	Х	X	X
Blood Spot		Х	X	X
Stool Sample		Х	X	X
Instructions for Drug Compliance		Х		
Drug Dispense		Х	X	
Discuss follow-up with primary hepatologist				Х
Adverse Events Review		Х	X	Х
Concomitant Medication Review	X	Х	X	Х
Assess Drug Accountability			X	X
Sub-study: Accelerometer		Х		Х

¹ The Baseline MRI will be conducted at the Baseline visit for those subjects with a historic liver biopsy or MRI. Subjects with just a historic ultrasound may have their baseline MRI conducted up to two weeks prior to the baseline visit (during the screening period).

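### Study product is to stop in pregnancy, but the only scheduled pregnancy test is at Week 0, so the second supply is handed out at Week 6 untested

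*Combined protocol and SAP*

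**What the plan says.** Section 4.11 (Unblinding Procedures) lists pregnancy as a condition under which the blind may be broken and states what happens to the product: "Pregnancy (study product discontinued". The synopsis, under Safety Monitoring, has the DSMB follow outcomes that include "abdominal pain, flatus, diarrhea, pregnancy, hepatotoxicity and any other outcomes".

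Testing appears once. The Week 0 procedures in section 4.1 include "Urine pregnancy test for females of childbearing potential". In Attachment 1 the row "Urine Pregnancy Test" has a single mark, in the Baseline column. The exclusion criterion in section 3.3 reads "Planned pregnancy, nursing an infant, confirmed or suspected to be pregnant between screening and time of study enrollment", so it stops at enrolment.

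Dispensing appears twice. Section 4.2 says "The research pharmacy will dispense the similarly appearing IMM-124E and placebo at baseline and again at Week 6". The Week 6 list in section 4.3 contains "Drug dispense from research pharmacy" and no pregnancy test.

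**The concern.** A stopping rule needs a way to be triggered. Here the one scheduled test falls before the first dose, when a positive result means the participant is not randomised. From then on, the rule works only if someone reports a pregnancy: through the adverse event review at Weeks 6 and 12, or through the telephone calls that sections 3.8 and 4.6 describe for tolerability and compliance.

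Participants are aged 6 to 19, and the Week 0 test shows that the plan expects some of them could be pregnant. An adolescent may not know, or may not say. Symptoms are a weak signal in this trial, because nausea is an expected product effect (sections 2 and 3.9) and section 4.9 presumes that gastrointestinal events within a set period of dosing are possibly product-related.

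At stake is whether the plan's own precaution can operate at the one moment when the study team actively hands over more product. The pregnancy outcome assigned to the DSMB is also never actively looked for during treatment.

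**Working it through.** The plan gives no figure to reproduce on this point. The check compares the schedules and then sizes the untested exposure.

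**Tests against dispensings**

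| Visit | Pregnancy test | Product dispensed | Source |
|---|---|---|---|
| Screening | no | no | 4.1, Attachment 1 |
| Week 0 | yes | yes | 4.1, 4.2, Attachment 1 |
| Week 6 | no | yes | 4.2, 4.3, Attachment 1 |
| Week 12 | no | no | 4.3, Attachment 1 |

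There is one test for two dispensings, and none at either post-baseline visit. The visit lists and Attachment 1 agree, so this is not a misread table. The blood schedule in Attachment 2 names no pregnancy test either.

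**Inputs**
- Treatment lasts 12 weeks, three doses of 600 mg daily (synopsis; section 3.6).
- Dispensing is at Weeks 0 and 6 (section 4.2). The size of each supply is not stated; I take each to last until the next visit.
- Timing: "Each study visit will have a visit window of ±5 days" (section 4.3).
- Enrolment is 40, over-enrolled by about 5, with equal recruitment by sex intended (section 3.5).

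**Planned exposure from the second supply**
- Whole course: 12 × 7 = 84 days; 84 × 3 = 252 doses.
- Second supply: 6 × 7 = 42 days; 42 × 3 = 126 doses.
- Share: 126 / 252 = 50%.

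**With the visit windows**
- Week 6 falls on day 42 ± 5, that is days 37 to 47. This is also the time since the only test.
- Week 12 falls on day 84 ± 5, that is days 79 to 89.
- Shortest Week 6 to Week 12 interval: 79 − 47 = 32 days, or 32 × 3 = 96 doses.
- Longest: 89 − 37 = 52 days, or 52 × 3 = 156 doses.

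**Longest dosing interval without a test**
- As planned: 84 days (79 to 89).
- With a Week 6 test: 42 days nominally, at most 52.

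**Participants needing the extra test**
- At equal recruitment: 40 / 2 = 20, or 45 / 2 = 22.5, about 23, with over-enrolment.
- The number is lower if more boys enrol, which section 3.5 allows, or if some girls in the 6 to 12 age group could not become pregnant.

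**The case against.** The best defence is that nothing here is contradictory. Section 4.11 concerns unblinding; its parenthesis says what follows once a pregnancy is known and promises no surveillance. Most of the DSMB outcomes listed beside pregnancy, such as nausea and flatus, are also captured by report. The plan tests at Week 0, reviews adverse events at Weeks 6 and 12, calls participants between visits and requires all untoward events to be documented (section 4.10). What remains is an unrecognised or undisclosed pregnancy within 12 weeks.

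The product is described as a medical food acting at the gut mucosa, and the placebo is milk protein. No fetal risk is documented and no pregnancy rate is given. The day and dose counts describe exposure, not risk; they rest on an inferred supply size, and only the active arm receives IMM-124E. Testing minors also raises disclosure and confidentiality issues.

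Much of this stands, and it limits the weight of the point. It does not close the gap. Nausea and flatus are noticed by the person who has them; an early pregnancy may not be. The sponsor already judged a test worthwhile before the first supply, and the documents give no reason for omitting it before the second. Testing minors is already part of the Week 0 procedures, so the issue is not new at Week 6.

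**Conclusion.** The concern holds. No scheduled test can trigger the on-treatment stop, and the plan as written allows a pregnant participant to be re-supplied for about half of the treatment period. That size assumes supplies lasting from visit to visit and attendance within the windows. How many participants could be affected is unknown: the documents give neither the number who could become pregnant nor an expected rate, and with 40 participants the count may be very small.

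This is a gap in safety procedure that should be closed because closing it is easy. It is not evidence of known harm.

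**What to change.** In section 4.3, add to the Week 6 list a urine pregnancy test for the same group tested at Week 0, with the result required before product is released. Mark the Week 6 column of the corresponding row in Attachment 1. State that a positive result means the second supply is withheld under section 4.11 and the participant stays in follow-up for the intention-to-treat analysis.

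Urine is the simpler choice. The 6 mL of serum already drawn at Week 6 (Attachment 2) would serve only if enough can be spared and the result is back before dispensing. A Week 12 test is optional: dosing is over by then, so it would only help ascertain the DSMB outcome.

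The cost is a minor amendment and one inexpensive test at an existing visit, with no added visit or blood draw. The downsides are a small burden on adolescent girls, a possible short wait before dispensing, and a check that consent and assent wording and the confidential handling of a positive result cover the second test. The fix is partial: pregnancies that begin after Week 6 would still be found only by report.
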